6.3.3 Restarting or increasing dose after hematological decline

Dosing may be restarted or increased following recovery of the hematologic parameter(s) to acceptable levels. [Table 6-4](#) illustrates the maximum allowable dose that may be used after restarting or increasing doses following a previous interruption or dose decrease.

Table 6-4 Ruxolitinib maximum allowable dose levels after dose interruption or reduction due to hematological decline

| Current Hb (g/dL) | Maximum allowable dose |
|------------------------------------|---|
| < 8 | Continue hold |
| 8 to < 10 | 5 mg bid for at least 2 weeks, if stable may increase to 10 mg bid |
| 10 to < 12 | 10 mg bid for at least 2 weeks, if stable may increase to 15 mg bid |
| ≥ 12 | 15 mg bid for at least 2 weeks, if stable may increase to 20 mg bid |
| Current PLT (x 10 ⁹ /L) | Maximum allowable dose |
| < 50 | Continue hold |
| 50 to < 75 | 5 mg bid for at least 2 weeks, if stable may increase to 10 mg bid |
| 75 to < 100 | 10 mg bid for at least 2 weeks, if stable may increase to 15 mg bid |
| ≥ 100 | 15 mg bid for at least 2 weeks, if stable may increase to 20 mg bid |
| Current ANC (x 10 ⁹ /L) | Maximum allowable dose |
| < 1.0 | Continue hold |
| 1.0 to < 1.5 | 5 mg bid for at least 2 weeks, if stable may increase to 10 mg bid |
| 1.5 to < 2.0 | 10 mg bid for at least 2 weeks, if stable may increase to 15 mg bid |
| ≥ 2.0 | 15 mg bid for at least 2 weeks, if stable may increase to 20 mg bid |

Dose increases should be in increments of 5 mg bid and should not occur more often than every 2 weeks.

When restarting ruxolitinib after dose interruption, the Hb, PLT, and ANC levels must be considered to determine the restart dose, regardless of which level caused the dose interruption. The lowest calculated dose per [Table 6-4](#) should be used. The restart dose should be at least 5 mg LESS than the dose that resulted in the interruption.

Patients who required dose interruption while receiving a dose of 5 mg bid may resume at a dose of 5 mg bid or 5 mg qd, but never higher, once:

- Hb is ≥ 10 g/dL
- PLT is $\geq 75 \times 10^9$ /L,
- and ANC is $\geq 1.5 \times 10^9$ /L

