6.1.1 Dosing regimen

The starting dose of ruxolitinib will be 10 mg bid (see [Section 6.3.4](#) and [Section 6.3.7](#) for exceptions). A standardized dosing paradigm will be used to determine dose adjustments for safety and efficacy so that each patient is titrated to their most appropriate dose (see [Section 6.3.1](#) of the protocol). The ruxolitinib dose should not exceed 25 mg bid and should not be less than 5 mg once a day unless there is an adverse event that warrants interruption.

Patients may self-administer daily ruxolitinib tablets qd or bid (see [Section 6.3.4](#) and [Section 6.3.7](#) for exceptions) orally, without regard to food, in an outpatient setting in accordance with the specified dosing schedule provided by the investigator.

Patients who miss a dose should be counseled to take the next dose as scheduled and not to take double the dose.

Table 6-1 Dose and treatment schedule

| Study treatments | Pharmaceutical form and route of administration | Dose | Frequency and/or Regimen |
|--------------------|---|--|--|
| INC424/ruxolitinib | Tablet for oral use | Starting dose 10 mg bid (approximately 12 hours apart: morning and night), to be increased or decreased (5 mg steps) per standardized dosing paradigm and not to exceed 25 mg bid (see Section 6.1.1) | Daily, unless instructed to temporarily withhold dosing for safety |

The investigator will instruct the patient to take the study drug as per protocol. All dosages prescribed and dispensed to the patient and all dose changes during the study should be recorded on the Dosage Administration Record eCRF.

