6.3 Dose modifications

6.3.1 Dose escalations due to inadequate efficacy

The initial dose of ruxolitinib will be 10 mg bid up to Week 4 (see [Section 6.3.4](#) and [Section 6.3.7](#) for exceptions). Based upon hematology and spleen palpation results, the dose of ruxolitinib **may** be increased by 5 mg bid from the previous 4 weeks in patients who meet the following conditions:

1. Inadequate efficacy as demonstrated by one or more of the following:

- a. Hct > 45%,
- b. WBC > upper limit of normal range,
- c. A clinically relevant increase in palpable spleen as determined by the investigator.

AND

2. The patient should have demonstrated adequate safety to increase the dose with all of the following:
 - a. Platelet count $\geq 140 \times 10^9/L$,
 - b. Hemoglobin $\geq 12 \text{ g/dL}$
 - c. ANC $\geq 1.5 \times 10^9/L$.
 - d. No treatment-related toxicity must have occurred with the current dose level, resulting in treatment reduction or interruption in the previous 28 days.

The total dose should never exceed 25 mg bid.

Table 6-2 Ruxolitinib allowed dose escalation due to inadequate efficacy

| Week of Study | Maximum Dose | Based on (no potent CYP3A4 inhibitor use) |
|---------------|--------------|---|
| 1 to 4 | 10 mg bid | Eligibility for study |
| 5 to 8 | 15 mg bid | Hematology, spleen palpation, AEs |
| 9 to 12 | 20 mg bid | Hematology, spleen palpation, AEs |
| 13 to EoT | 25 mg bid | Hematology, spleen palpation, AEs |

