6.3.7 Dose reduction for concomitant CYP inhibitor use

Ruxolitinib is metabolized in the liver by the cytochrome (CYP) P450 metabolizing enzyme system, predominantly by the CYP 3A4 isozyme. With concomitant dosing of potent CYP3A4 inhibitors such as systemic ketoconazole, plasma exposure of ruxolitinib increases by approximately 2-fold. Thus, a dose reduction of ~ 50% for ruxolitinib is appropriate for patients who take systemic ketoconazole or other potent CYP3A4 inhibitors systemically as concomitant medication (see [Appendix 7](#)).

Potent inhibitors of CYP3A4 include systemic ketoconazole, clarithromycin, itraconazole, nefazodone and telithromycin. The use of these agents on Study Day 1 will require that patients initiate ruxolitinib therapy at 10 mg qd.

NOTE: once the course of therapy using a potent CYP3A4 inhibitor has been completed, the patient may resume his/her prior bid dose regimen of ruxolitinib beginning the next day.

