6.4.2 Permitted concomitant therapy requiring caution and/or action

The following medications have restrictions on use, dose, or require changes to the way in which ruxolitinib is administered during the study:

- Systemic corticosteroid doses greater than the equivalent of 10 mg prednisolone per day is not permitted, unless used as part of a ruxolitinib-dose tapering strategy (see [Section 6.3.8 Optional dose tapering strategy in the event of discontinuation](#))
- Low dose aspirin (75-150 mg/day) and non-steroidal anti-inflammatory agents (acetaminophen, ibuprofen) may be used. Higher doses of aspirin (> 150 mg/day) should not be used except when medically indicated and recommended by the treating physician.
- When concomitant administration of an anticoagulant/antiplatelet medication is required for patient management, the platelet count history, and any observations of thrombocytopenia during the study while on study drug should be considered.
- Granulocyte growth factors are not allowed while study medication is being administered but may be used for severe neutropenia at the Investigator's discretion while study medication is being withheld.
- Inducers or inhibitors of the metabolizing enzyme CYP3A4 (Refer to [Appendix 7](#)):
- When concomitant administration of a strong (potent) systemic inhibitor of CYP3A4 metabolizing enzymes or dual CYP2C9/CYP3A4 inhibitors (see [Appendix 7](#)) is required for patient management, the dose of study treatment must be reduced by approximately 50% to be administered twice daily by decreasing the twice daily dose or by decreasing the frequency of dosing to the corresponding once daily dose when twice daily dosing is not practical.

- Note: No dose adjustment of ruxolitinib is needed for use with topical ketoconazole.
- Note: More frequent monitoring of hematology parameters and clinical signs and symptoms of ruxolitinib related adverse reactions is recommended upon initiation of a strong (potent) CYP3A4 inhibitor.
- No dose adjustment will be made when moderate systemic CYP3A4 inducers (See [Appendix 7](#)) are co-administered with study treatment.

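### The restart rules in Protocol 6.3.2 and 6.3.3 do not fit the once-daily regimens the protocol itself creates, and they conflict after a hold on 10 mg qd or 5 mg qd

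*Protocol*

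**What the plan says.** **Where once-daily dosing comes from**
- Protocol 6.3.7, on potent CYP3A4 inhibitors: "The use of these agents on Study Day 1 will require that patients initiate ruxolitinib therapy at 10 mg qd".
- Protocol 6.4.2 requires a cut of about 50% with a strong systemic inhibitor. One way to achieve it is "by decreasing the frequency of dosing to the corresponding once daily dose when twice daily dosing is not practical". No values are listed.
- Protocol 6.1.1 sets a floor: the dose "should not be less than 5 mg once a day unless there is an adverse event that warrants interruption".
- Protocol 6.3.3: "Patients who required dose interruption while receiving a dose of 5 mg bid may resume at a dose of 5 mg bid or 5 mg" (the second option is once daily), never higher, and only once Hb, platelets and ANC have reached stated levels.

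**How restart is written**
- Protocol 6.3.2 allows a restart at 5 mg twice daily when counts recover, whatever the earlier regimen.
- Protocol Table 6-4 gives maximum doses by count. Its lowest tier reads "5 mg bid for at least 2 weeks, if stable may increase to 10 mg bid" and the next "10 mg bid for at least 2 weeks, if stable may increase to 15 mg bid". The top tier starts at 15 mg bid. There is no once-daily entry.
- Protocol 6.3.3 adds the decrement: "The restart dose should be at least 5 mg LESS than the dose that resulted in the interruption".
- Table 6-2 heads its last column "Based on (no potent CYP3A4 inhibitor use"). Table 6-4 carries no such limit.

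**What bears on the basis of the decrement**
- The protocol glossary describes a dose level as a total daily (or weekly) amount, and the title of Table 6-4 speaks of dose levels.
- SAP 2.4.6.2 defines both reduction and increase on total daily dose.
- Against that, 6.3.3 expresses dose increases in steps of 5 mg bid, which suggests a per-administration basis.

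**The concern.** The restart rules are there to bring a patient back on a suitably cautious dose after a hematologic hold. For a patient held on a once-daily regimen, the written rules disagree with one another, and at least one of them does not lower the daily dose. Two sites following the text could restart the same patient on different daily doses, and both could defend it.

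This bears on patient safety first. It also bears on the data: adverse events and hematology make up the primary objective, SAP 2.4.6.2 counts dose changes, and SAP 2.4.3 has a deviation category for an incorrect dose. A restart that a site regards as a compliant reduction could be tabulated as no reduction. An incorrect restart dose cannot be judged consistently while the rule is undefined.

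**Working it through.** The plan states no figure to reproduce. The check converts each rule to mg/day and compares it with the dose at the hold.

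**Inputs.** Holds on 10 mg qd (6.3.7) and 5 mg qd (6.1.1, 6.3.3); restart at 5 mg bid (6.3.2); initial tiers of 5, 10 and 15 mg bid (Table 6-4); decrement of at least 5 mg (6.3.3); cut of about 50% with a strong inhibitor (6.4.2).

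**Step 1: the 6.3.2 restart alone.** Daily dose = 5 × 2 = 10 mg/day.
- After 10 mg qd: 10 / 10 = 1, the same daily dose.
- After 5 mg qd: 10 / 5 = 2, double the daily dose.

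This step needs no reading of the decrement.

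**Step 2: the 6.3.3 decrement**, with d the once-daily dose at the hold and tier the Table 6-4 dose per administration.
- Total-daily reading: at most min(2 × tier, d − 5). For d = 10: min(10, 20 or 30; 5) = 5 mg/day. For d = 5: 0.
- Per-administration reading, given bid as in Table 6-4: at most 2 × min(tier, d − 5). For d = 10: 2 × 5 = 10 mg/day in all three tiers. For d = 5: 0.
- The 6.4.2 cut applied to the tiers by giving them once daily: at most min(tier, d − 5). For d = 10: 5 mg/day. For d = 5: 0.

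| Held on | 6.3.2 restart | Decrement, total daily | Decrement, per administration | 6.4.2 cut applied to Table 6-4 |
|---|---|---|---|---|
| 10 mg qd | 10 mg/day (same) | at most 5 | at most 10 (same) | at most 5 |
| 5 mg qd | 10 mg/day (double) | 0 | 0 | 0 |

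After 10 mg qd, the total-daily reading puts 6.3.2 (10 mg/day) and 6.3.3 (at most 5 mg/day) in conflict. On the per-administration reading they agree, but neither requires a lower daily dose. After 5 mg qd they conflict on every reading: 10 mg/day against nothing, with the 6.1.1 floor at 5 mg/day.

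**Step 3: the same daily dose, split differently.**

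| | Held on 5 mg bid (10 mg/day) | Held on 10 mg qd (10 mg/day) |
|---|---|---|
| Governing text | Special rule closing 6.3.3 | Table 6-4 and the decrement |
| Hb to restart (g/dL) | ≥ 10 | from 8 |
| Platelets to restart (×10⁹/L) | ≥ 75 | from 50 |
| ANC to restart (×10⁹/L) | ≥ 1.5 | from 1.0 |
| Ceiling afterwards | 5 mg bid | Lowest tier: 10 mg bid after at least 2 stable weeks |

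The right-hand ceiling is 10 × 2 = 20 mg/day, twice the interrupted 10 mg/day, before any 6.4.2 cut. The decrement limits the restart dose, not this later increase.

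**Step 4: check on bid patients.** With equal bid doses in 5 mg steps (Table 6-1), the smallest possible reduction is 5 mg per administration, or 10 mg/day; for example, 10 mg bid to 5 mg bid is 20 to 10 mg/day. Both readings of the decrement are met. The missing basis therefore matters only for once-daily patients, the group Table 6-4 does not cover.

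**The case against.** A reader might infer that every restart is twice daily and that once-daily patients will therefore restart on the same or a higher daily dose. The documents do not support that.

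- Section 6.3.3 does contain a 5 mg qd restart, although only for patients held on 5 mg bid.
- Table 6-4 gives maxima, restart is permissive, and the decrement is a minimum. An investigator may always go lower.
- On the total-daily reading, which the glossary and SAP 2.4.6.2 favor, the decrement lowers the daily dose wherever it leaves a dose at all.
- Calculating increases after 15 to 25 mg qd would require doses that no section lists, plus the per-administration reading.
- Arguing that Table 6-4 lets inhibitor patients exceed the exposure of the 25 mg bid limit would set aside the mandatory cut of about 50% in 6.4.2.

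Other points narrow the reach. Exclusion criterion 5 bars strong CYP3A4 inhibitors at screening, and 6.4.2 recommends closer hematology monitoring when one is started. The 6.1.1 floor has its own exception for adverse events that warrant interruption. Section 6.3.6 requires permanent discontinuation in some cases where no lower restart dose is available, though its heading limits it to non-hematological safety. The trial is single-arm and descriptive, so no hypothesis test is affected, and a claim that the rule will itself produce repeat cytopenias would be speculation.

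All of this stands as a limit on size. None of it reconciles 6.3.2 with 6.3.3, says what follows a hold on 5 mg qd, explains the different treatment of the two 10 mg/day regimens, or says how the 6.4.2 cut acts on Table 6-4.

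**Conclusion.** The point holds as an inconsistency among stated rules, which is more than a missing detail. Three parts do not depend on how the decrement is read: the 6.3.2 restart is the same daily dose after 10 mg qd and double after 5 mg qd; the decrement leaves 0 mg after 5 mg qd; and two patients on 10 mg/day have different thresholds and ceilings according to how the dose is split. One part does depend on it: whether 6.3.3 lowers the daily dose after 10 mg qd (yes on a total-daily basis, not necessarily per administration).

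It is not established that any patient would be restarted too high, and no dose is judged right or wrong here. The comparison takes each rule at the most it permits. The number of once-daily patients is not given; it is probably small given exclusion criterion 5, although 6.3.7 provides for inhibitor use on Day 1 and 6.4.2 for inhibitors needed during the study. The matter is worth correcting because it concerns dosing after a hematologic hold and the remedy is cheap.

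**What to change.** Amend the protocol wording so that 6.1.1, 6.3.2, 6.3.3 with Table 6-4, 6.3.7 and 6.4.2 agree for patients on once-daily dosing:

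1. State whether the 5 mg decrement is per administration or on total daily dose, consistently with the definition of reduction in SAP 2.4.6.2.
2. State how the cut of about 50% in 6.4.2 applies to the Table 6-4 tiers, or give that table an inhibitor qualifier as Table 6-2 has.
3. Say which restart thresholds and ceilings apply after a hold on 10 mg qd, given those for 5 mg bid.
4. Resolve the conflict between 6.3.2, 6.3.3 and the 6.1.1 floor after a hold on 5 mg qd.

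The clinical team decides the doses. The cost is a protocol amendment to a few dosing paragraphs and one table, with no new assessments or patients. The SAP definition can stay as it is if the protocol adopts the same basis.

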6.3.4 Ruxolitinib starting dose for patients with platelets less than 100x10⁹/L

Patients who enter the study with a platelet value between $50 \times 10^9/\text{L}$ and $<100 \times 10^9/\text{L}$ should start ruxolitinib with a starting dose of 5mg bid. It is recommended that these patients' platelet values are monitored more frequently per [Table 6-3](#).

6.3.5 Dose modification for renal impairment

No specific dose adjustment is needed in patients with mild or moderate renal impairment while receiving ruxolitinib.

Patients diagnosed with severe renal impairment while receiving ruxolitinib should be carefully monitored and need to have their doses reduced to avoid adverse drug reactions (ADRs).

6.3.6 Dose reduction for non-hematological safety

Study drug MUST be permanently discontinued upon the occurrence of a clinically significant Grade 3 or Grade 4 laboratory or non-laboratory abnormality attributed to ruxolitinib if fails to resolve to Grade 2 or better within 8 weeks or if a lower re-start dose or administration schedule is either not available or likely to be clinically ineffective.

6.3.7 Dose reduction for concomitant CYP inhibitor use

Ruxolitinib is metabolized in the liver by the cytochrome (CYP) P450 metabolizing enzyme system, predominantly by the CYP 3A4 isozyme. With concomitant dosing of potent CYP3A4 inhibitors such as systemic ketoconazole, plasma exposure of ruxolitinib increases by approximately 2-fold. Thus, a dose reduction of ~ 50% for ruxolitinib is appropriate for patients who take systemic ketoconazole or other potent CYP3A4 inhibitors systemically as concomitant medication (see [Appendix 7](#)).

Potent inhibitors of CYP3A4 include systemic ketoconazole, clarithromycin, itraconazole, nefazodone and telithromycin. The use of these agents on Study Day 1 will require that patients initiate ruxolitinib therapy at 10 mg qd.

NOTE: once the course of therapy using a potent CYP3A4 inhibitor has been completed, the patient may resume his/her prior bid dose regimen of ruxolitinib beginning the next day.

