5.3 Exclusion criteria

Patients eligible for this study should not meet **any** of the following criteria at screening:

Lab and Clinical Abnormalities

1. Subjects with known hypersensitivity to ruxolitinib or any of its excipients
2. Patients with severely impaired renal function defined by:
Serum creatinine > 2 mg/dL ($> 176.8\mu\text{mol/L}$)
3. Patients with inadequate liver function defined by any of these:
 - Total bilirubin $\geq 2.5 \times$ ULN and subsequent determination of direct bilirubin $\geq 2.5 \times$ ULN;
 - Alanine aminotransferase (ALT) $> 2.5 \times$ ULN; Aspartate aminotransferase (AST) $> 2.5 \times$ ULN.
4. Platelet counts $< 50 \times 10^9/\text{L}$ or an Absolute Neutrophil Count (ANC) $< 1 \times 10^9/\text{L}$ at screening.

Concurrent Diseases / Medication History

5. Patients being treated concurrently with a strong (potent) systemic inhibitor or inducer of CYP3A4 (refer to [Appendix 7](#)) at the time of Screening.
6. Presence of active bacterial, fungal, parasitic, or viral infection which requires therapy.

7. Known history of human immunodeficiency virus (HIV) infection or other immunodeficiency syndromes such as X-linked agammaglobulinemia and common variable immune deficiency
8. Acute viral hepatitis or active chronic hepatitis B or C infection.
9. History of progressive multifocal leuko-encephalopathy (PML).
10. Impairment of gastrointestinal (GI) function or GI disease that may significantly alter the absorption of ruxolitinib (e.g., ulcerative diseases, uncontrolled nausea, vomiting, diarrhea, malabsorption syndrome, small bowel resection).
11. History or current diagnosis of uncontrolled or significant cardiac disease, including any of the following:
 - Myocardial infarction within last 6 months
 - Uncontrolled congestive heart failure
 - Unstable angina within last 6 months
 - Clinically significant (symptomatic) cardiac arrhythmias (e.g., sustained ventricular tachycardia, and clinically significant second or third degree AV block without a pacemaker)
12. Significant concurrent, uncontrolled medical condition which, in the investigator's opinion, would jeopardize the safety of the patient or compliance with the protocol.
13. Subjects undergoing treatment with another investigational medication or having been treated with an investigational medication within 30 days or 5 half-lives (whichever is longer) prior to the first dose of study drug.

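### The fixed Day 1 dose of 10 mg once daily with a potent CYP3A4 inhibitor gives low-platelet starters no dose cut at all

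*Protocol*

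**What the plan says.** Five parts of the protocol bear on the starting dose.

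- **6.1.1, standard start:** "The starting dose of ruxolitinib will be 10 mg bid". Sections 6.3.4 and 6.3.7 are listed together as exceptions. The same section sets a floor: the dose "should not be less than 5 mg once a day", apart from interruption for an adverse event.
- **6.3.4, low platelets:** patients entering with platelets from 50 to below 100 x 10^9/L "should start ruxolitinib with a starting dose of 5mg bid". They are eligible, because exclusion 4 bars only counts below 50 x 10^9/L.
- **6.3.7, potent CYP3A4 inhibitors:** exposure rises about 2-fold and a reduction of about 50% is appropriate. For the first day: "The use of these agents on Study Day 1 will require that patients initiate ruxolitinib therapy at 10 mg qd". No platelet condition is attached.
- **6.4.2, concomitant therapy:** with a strong inhibitor "the dose of study treatment must be reduced by approximately 50" per cent, either by lowering the twice-daily dose or "by decreasing the frequency of dosing to the corresponding once daily dose when twice daily dosing is not practical".
- **5.3, exclusions:** criterion 5 excludes "Patients being treated concurrently with a strong (potent) systemic inhibitor or inducer of CYP3A4", judged at Screening. Criterion 6 excludes "Presence of active bacterial, fungal, parasitic, or viral infection which requires therapy".

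**The concern.** The Day 1 instruction fixes an absolute dose, while the reason given for it is a relative cut. The two agree only for a patient whose start would otherwise be 10 mg twice daily. A patient who meets both exceptions, with low platelets and an inhibitor on Day 1, has a start of 5 mg twice daily before the inhibitor is considered. For that patient 10 mg once daily is the same daily dose in a different schedule.

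Section 6.1.1 names the two exceptions side by side and does not say what to do when both apply. The investigator then has two mandatory instructions with different answers: 10 mg once daily from 6.3.7, and 5 mg once daily from the 50% rule in 6.4.2. Protocol section 12 permits no authorized deviations, and SAP 2.4.3 lists an incorrect dose among the reportable deviation categories, so either choice can be faulted.

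What is at stake is initial dosing safety in the entrants with the least platelet reserve, on a drug whose known toxicity includes thrombocytopenia.

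**Working it through.** **Inputs**

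- Standard start: 10 mg twice daily = 20 mg/day (6.1.1).
- Low-platelet start: 5 mg twice daily = 10 mg/day (6.3.4).
- Day 1 dose with a potent inhibitor: 10 mg once daily = 10 mg/day (6.3.7).
- Inhibitor effect on AUC: f = 2, approximate (1.2.1.2 and 6.3.7). The documents give no interval, so I also show f = 1.5 and f = 2.5 as an assumed range.
- AUC is taken as proportional to daily dose, since 1.2.1.2 reports linear pharmacokinetics from 5 to 200 mg.

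**Formulas**

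- Dose cut = 1 − (daily dose with inhibitor ÷ applicable starting daily dose).
- AUC ratio = (daily dose with inhibitor × f) ÷ applicable starting daily dose without inhibitor.

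**Step 1: reproduce the plan's own figure.** For the standard start, cut = 1 − 10/20 = 50%, which matches the roughly 50% in 6.3.7. The AUC ratio is 10 × 2 / 20 = 1.0, so the inhibitor is fully offset.

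**Step 2: apply the same sentence to the low-platelet start.** Cut = 1 − 10/10 = 0%. AUC ratio = 10 × 2 / 10 = 2.0.

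**Step 3: apply the 50% rule of 6.4.2 to the low-platelet start.** The corresponding once-daily dose is 5 mg, which is at the 6.1.1 floor and so allowed. Cut = 1 − 5/10 = 50%. AUC ratio = 5 × 2 / 10 = 1.0.

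| Start without inhibitor | Day 1 dose with inhibitor | Cut | AUC ratio, f = 1.5 | f = 2 | f = 2.5 |
|---|---|---|---|---|---|
| 10 mg twice daily | 10 mg once daily (6.3.7) | 50% | 0.75 | 1.0 | 1.25 |
| 5 mg twice daily | 10 mg once daily (6.3.7) | 0% | 1.5 | 2.0 | 2.5 |
| 5 mg twice daily | 5 mg once daily (6.4.2) | 50% | 0.75 | 1.0 | 1.25 |

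**Step 4: can the overlap occur?** Exclusion 5 is judged at Screening, 7.1.1 runs the screening period to Day -1, and 7.1.1.1 requires eligibility during that phase. An inhibitor begun after the eligibility check is not caught, and 6.3.7 expressly provides for use on Day 1. The overlap is therefore possible but rare.

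**The case against.** The strongest reply is that the right rule is already in the protocol. Section 6.4.2 is mandatory, works from the patient's own dose and is not limited to the period after Day 1. The sentence just before the Day 1 instruction in 6.3.7 states the same 50% principle. On that reading, 10 mg once daily merely illustrates the principle for the default start, and a careful investigator would give 5 mg once daily. This is a fair account of the likely intent. It does not settle the text: the Day 1 sentence is the more specific instruction, it is worded as a requirement, and 6.4.2 neither overrides it nor refers to it.

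Second, the resulting exposure is not extreme. Ten mg once daily with a 2-fold effect is equivalent to 20 mg/day, the same as a standard start. After an interruption or reduction, Table 6-4 allows up to 10 mg twice daily at once for platelets of 75 to below 100 x 10^9/L, and after at least two stable weeks on 5 mg twice daily for 50 to below 75. This stands as context. Those are restart ceilings, however, not starting doses, and exposure equal to a standard start is still twice what 6.3.4 chose for these patients.

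Third, very few patients would be affected. Raised platelet counts are common in this disease (1.1), exclusion 5 removes inhibitor users at Screening, and exclusion 6 removes patients with active infection needing therapy, although most of the agents named in 6.3.7 are anti-infectives. This stands, and it is one reason why the point is minor.

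Fourth, there are safeguards: closer monitoring is recommended in 6.3.4 and 6.4.2, dose reduction is to be considered below 100 x 10^9/L, and treatment is to be interrupted below 50 x 10^9/L. These limit harm. But interruption acts only after platelets have fallen, and Table 6-3, to which 6.3.4 points for monitoring, gives no interval.

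**Conclusion.** The concern holds, as a minor point. As written, 6.3.7 gives low-platelet starters a 0% cut where it says about 50% is appropriate, and about 2.0 times the AUC intended by 6.3.4 (1.5 to 2.5 times over the assumed range for the inhibitor effect). The standard start is handled correctly.

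The daily-dose arithmetic is exact. The exposure figure rests on linear pharmacokinetics and on an approximate 2-fold effect taken from single doses with ketoconazole. It concerns AUC only, not peak or trough. The documents give no count of affected patients, and whether any would actually receive 10 mg once daily depends on which section the investigator follows. No endpoint or analysis changes.

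**What to change.** Replace the Day 1 sentence in 6.3.7 with wording such as: *Use of a potent CYP3A4 inhibitor on Day 1 halves the applicable starting dose: 10 mg bid becomes 10 mg qd, and 5 mg bid under Section 6.3.4 becomes 5 mg qd.*

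This brings the Day 1 rule into line with 6.4.2, stays at the permitted minimum and settles the case where both exceptions apply. The note in 6.3.7 on resuming the earlier dose can stay as it is. The cost is one sentence at the next amendment, with no change to visits, data collection or analysis.

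### The fixed Day 1 dose of 10 mg qd with a potent CYP3A4 inhibitor (Protocol 6.3.7) gives no dose reduction to patients whose low platelets already put them on 5 mg bid

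*Protocol*

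**What the plan says.** The standard start is 10 mg bid. Sections 4.1 and 6.1.1 name Sections 6.3.4 and 6.3.7 together as the exceptions.

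- **Section 6.3.4 (low platelets).** Patients entering with platelets from 50 to <100 × 10⁹/L "should start ruxolitinib with a starting dose of 5mg bid". They can enroll, because exclusion criterion 4 bars only counts below 50.
- **Section 6.3.7 (potent CYP3A4 inhibitors).** With such an inhibitor, "plasma exposure of ruxolitinib increases by approximately 2-fold". The section concludes that "a dose reduction of ~ 50% for ruxolitinib is appropriate for patients who take systemic ketoconazole or other potent CYP3A4 inhibitors systemically". For use at the start of treatment it gives one dose, without a platelet condition: "The use of these agents on Study Day 1 will require that patients initiate ruxolitinib therapy at 10 mg qd".
- **Section 6.4.2 (co-administration).** When a strong inhibitor is needed for patient management, "the dose of study treatment must be reduced by approximately 50" percent, through a smaller bid dose or, where bid dosing is impractical, the matching once-daily dose.
- **Section 5.3.** Exclusion criterion 5 covers "Patients being treated concurrently with a strong (potent) systemic inhibitor or inducer of CYP3A4" at the time of screening.

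No section says what applies to a patient who meets both exceptions.

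**The concern.** The 10 mg qd figure was evidently derived from the 10 mg bid start. Applied to a patient whose start is 5 mg bid, it moves the same daily amount from two doses to one and reduces nothing. The protocol halves the start because platelets are low, then in effect cancels that protection when the inhibitor doubles exposure.

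The patients concerned have the least platelet reserve of any who may enroll. At 50 to <75 × 10⁹/L they are less than 25 × 10⁹/L above the count at which Table 6-3 interrupts treatment. The wording is also mandatory. An investigator who sensibly gives 5 mg qd departs from the sentence in 6.3.7, Section 12 permits no authorized deviations, and SAP Section 2.4.3 lists an incorrect dose as a reportable deviation category.

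**Working it through.** **Inputs**

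- Standard start: 10 mg bid (Protocol 6.1.1)
- Start at platelets 50 to <100 × 10⁹/L: 5 mg bid (6.3.4)
- Day 1 dose with a potent inhibitor: 10 mg qd (6.3.7)
- Intended reduction: about 50% (6.3.7)
- Exposure multiplier with a potent inhibitor: about 2 (6.3.7)
- Lowest allowed dose: 5 mg qd (6.1.1)

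**1. Reduction in total daily dose** = 100 × (1 − new daily dose / usual daily dose)

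| Patient | Usual start | Dose with inhibitor | Reduction |
|---|---|---|---|
| Standard | 10 × 2 = 20 mg/day | 10 × 1 = 10 mg/day | 100 × (1 − 10/20) = 50% |
| Low platelets, as written | 5 × 2 = 10 mg/day | 10 × 1 = 10 mg/day | 100 × (1 − 10/10) = 0% |
| Low platelets, 5 mg qd | 5 × 2 = 10 mg/day | 5 × 1 = 5 mg/day | 100 × (1 − 5/10) = 50% |

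The first row reproduces the protocol's own figure. The second shows that it fails for the low-platelet start. The third meets the rule and sits exactly at the 6.1.1 minimum.

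**2. Exposure, as the equivalent daily dose without an inhibitor** = daily dose × multiplier

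- As written: 10 × 2 = 20 mg/day-equivalent, the same as 10 mg bid alone. Against the 6.3.4 start: 20/10 = 2.0.
- With 5 mg qd: 5 × 2 = 10 mg/day-equivalent. Ratio 10/10 = 1.0.
- If the multiplier is assumed to lie between 1.8 and 2.2, the ratio as written is 1.8 to 2.2, and with 5 mg qd it is 0.9 to 1.1.

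Because the two daily doses are equal, the ratio as written is simply the inhibitor's multiplier.

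**3. Benchmark: the platelet caps in Table 6-4.** These govern dosing after a hematological hold or reduction, not first doses, so they serve only as a yardstick. For 50 to <75 the cap is "5 mg bid for at least 2 weeks, if stable may increase to 10 mg bid"; for 75 to <100 it is 10 mg bid from the outset.

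| Platelets (× 10⁹/L) | Cap, mg/day | As written (20) | With 5 mg qd (10) |
|---|---|---|---|
| 50 to <75, first 2 weeks | 5 × 2 = 10 | 2.0 | 1.0 |
| 50 to <75, after 2 stable weeks | 10 × 2 = 20 | 1.0 | 0.5 |
| 75 to <100, from the outset | 10 × 2 = 20 | 1.0 | 0.5 |

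Against this yardstick the excess is confined to the lower platelet band in the first two weeks.

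**4. How the case can arise.** Exclusion criterion 5 bars the inhibitor at screening. Criterion 6 bars active infection needing therapy, and four of the five agents named in 6.3.7 are anti-infectives. Section 7.1.1.1 requires confirmed eligibility before treatment. What remains is an inhibitor started after screening and in use on Day 1. The gap is at most 14 days where screening labs serve as baseline (4.1), up to 35 days where labs are repeated (4.1, 7.2.2.5), and Day 1 alone if no exclusion may be met at any time in the screening phase.

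**The case against.** The strongest reply is that Section 6.4.2 already handles this. Its rule is mandatory and relative to the patient's dose, it does not expressly leave out Day 1, and for a 5 mg bid patient its once-daily route leads to 5 mg qd. Section 6.3.7 itself states the 50% principle just before the fixed dose. On this view the flaw is an unstated interaction that a careful reader would resolve correctly.

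That stands only in part. Section 6.4.2 speaks of reducing a dose and can be read as covering on-treatment use alone, in which case nothing corrects 6.3.7. If it does reach Day 1, it contradicts an explicit instruction in 6.3.7 and nothing ranks the two.

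Other points are fair and limit the size of the problem:

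- The patient must meet two uncommon conditions at once. Section 1.1 notes that raised platelet counts are common in PV, and Section 6.4 tells patients not to take additional medication without consulting the investigator.
- The 2-fold figure comes from single-dose data with ketoconazole (1.2.1.2), and the 0% refers to total daily dose; the schedule does change from bid to qd.
- The platelet requirement of ≥140 × 10⁹/L in 6.3.1, under "The patient should have demonstrated adequate safety to increase the dose with all of the following", concerns escalation for inadequate efficacy. It shows how cautious the protocol is about the step from 5 to 10 mg bid but does not govern the first dose.
- Table 6-3 says to consider reduction below 100 × 10⁹/L, and Sections 6.3.4 and 6.4.2 recommend closer blood count monitoring. These act after the first dose; they do not set it.
- No endpoint, analysis set or estimate depends on this dose.

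**Conclusion.** The concern holds. Section 6.3.7 does not deliver its own reduction of about 50% to patients starting at 5 mg bid: it orders 10 mg/day where the rule gives 5 mg/day. Expected exposure is about twice that of the intended low-platelet start, taking the protocol's 2-fold multiplier at face value and total daily dose as the measure of exposure.

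The number of patients affected cannot be estimated from the documents and is probably very small. The consequence is for individual safety, not for inference. Because safety is the primary objective and following the text gives the wrong first dose to a vulnerable group, this should be corrected, not left to clinical judgment.

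**What to change.** In Protocol Section 6.3.7, directly after the 10 mg qd Day 1 dose, add: (5 mg qd if the starting dose under Section 6.3.4 is 5 mg bid).

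The same edit could close a small gap in that section's closing note, which lets patients return to their prior bid regimen once the inhibitor course ends. A patient who began on qd has no prior bid regimen, so the note should point to the bid start the patient would otherwise have had.

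The cost is one parenthetical, and optionally one clause, at the next amendment. Sections 6.1.1 and 6.3.3 already allow 5 mg qd, so no new tablet strength, visit or data item is needed, and the SAP does not change.
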